# Research Protocol

Title: "Medical Cannabis as an Opiate alternative"

NCT number: not yet assigned

Protocol ID 856134

Date of Document: October 11, 2024

Purpose:

Opioid use for pain has increased drastically over last decade with disastrous results that lead to an epidemic of overdoses and deaths in the United States. Philadelphia has been described as "ground zero" in the opiate epidemic of overdoses and deaths in the United States. Some initial clinical experience shows that medical marijuana can potentially assist patients suffering from certain serious medical conditions by alleviating pain and improving quality of life, allowing them to discontinue opiates.

Medical Cannabis is very safe and a viable option for pain relief to improve patients and their family's quality of life. The medical marijuana law in Pennsylvania was passed in 2016 with the hope that this might alleviate the opiate crisis. The opioid death rate in Pennsylvania was 37.9 per 100,000 people. However, medical cannabis is not covered by insurance and is an out of pocket expense. This has been a barrier to some patients trying medical cannabis as an alternative. This can create a disparity in care of chronic pain patients.

Methods:

Recruitment and inclusion/exclusion criteria: Potential participants will be recruited from an outpatient chronic pain clinic. 40 patients who have agreed to attempt wean down on opioid medication and have a diagnosis which qualifies them for medical marijuana will be selected for our study. In these selected patients cost of the treatment was the main barrier for starting medical cannabis. Each participant will undergo a urine drug screen, a pain assessment using the visual analog scale and pain quality will be assessed using the SF-36 health related

quality and McGill Pain Questionnaire, which measures sensory, affective and evaluative dimensions of pain prior to receiving medical marijuana and then at 6 months.

Each patient will be evaluated by a physician who is certified to evaluate patients for Medical Cannabis. If the patient qualifies for Medical Cannabis the next step is for the patient to register on the state of Pennsylvania medical marijuana website. Medical conditions that qualify patient in the states of Pennsylvania for medical marijuana are ALS, Cancer, Crohn's MS, Neurodegenerative diseases, neuropathies, chronic or intractable pain of neuropathic origin. After the patient registers the physician will also certify them on the website. After the patients are certified they will apply for medical marijuana card. Once the patient receives a medical marijuana card the patient will start an opioid weaning plan. Each patient will have an individualized plan for weaning off their opioids which is their standard care plan. The patient will go to the select medical marijuana dispensary and will be able to choose their medical cannabis product. The Curaleaf medical cannabis dispensary will have a list of patients and they will be able to choose from the cannabis products. The patient will be followed up monthly for six months by physician and he will assess the patient's pain levels and Medical Cannabis doses and opioid doses monthly. We will also note the patient side effects, tolerance and any decrease in symptoms. At six months the physician will recheck a urine drug screen, current pain level and readminister the McGill Pain Questionnaire and SF-36 health related quality. The Medical Cannabis doses and strains will be noted.

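### No side-effect reading is listed before cannabis starts, so side effects noted at the monthly visits cannot be sorted into pre-existing and new

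*Protocol*

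**What the plan says.** The Protocol, Methods, describes one group: "40 patients who have agreed to attempt wean down on opioid medication and have a diagnosis which qualifies them for medical marijuana will be selected". No comparator is described.

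The same section lists the assessments and their timing. The list opens with "Each participant will undergo a urine drug screen, a pain assessment using the visual analog scale and pain quality will be assessed using the SF-36" and closes with "McGill Pain Questionnaire, which measures sensory, affective and evaluative dimensions of pain prior to receiving medical marijuana and then at 6 months". Side effects are not on it. Later in Methods, the six-month recheck names the same four items: urine screen, pain level, McGill and SF-36.

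The Methods text then gives this sequence:

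- The wean: "Once the patient receives a medical marijuana card the patient will start an opioid weaning plan".
- The cannabis: "The patient will go to the select medical marijuana dispensary and will be able to choose their medical cannabis product".
- Monthly physician follow-up for six months, with pain levels, cannabis doses and opioid doses assessed each month.
- Within that follow-up: "We will also note the patient side effects, tolerance and any decrease in symptoms".

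No rule is given for assigning a side effect to a cause. Under Purpose, the protocol states as background that "Medical Cannabis is very safe and a viable option for pain relief".

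**The concern.** A side effect first written down at a monthly visit may have been present for years under opioids, may come from the wean, or may come from cannabis. A reading taken before either change would identify the first kind. The protocol lists no such reading, so a long-standing complaint and a new one look the same in the record.

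The gap also works in the other direction. The study is about an alternative to opioids, and one natural benefit of such an alternative is that opioid side effects fade. Showing that they fade requires knowing who had them at the start. The note on any decrease in symptoms is a change measure, and outside pain and the SF-36 domains it has no recorded starting point.

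This cannot be left to an analysis plan. Which data are collected at which visit is fixed by the protocol, and no later analysis can recover a baseline that was never taken.

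**Working it through.** The plan gives no side-effect rate and no derivation of the sample size, so there is no stated figure to reproduce. The check is a comparison of what is collected when, followed by an illustration of size.

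**What is collected when (Protocol, Methods)**

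| Item | Before cannabis | Monthly | Six months |
|---|---|---|---|
| Urine drug screen | yes | not stated | yes |
| Pain level | yes (VAS) | yes | yes |
| SF-36 | yes | not stated | yes |
| McGill | yes | not stated | yes |
| Cannabis and opioid doses | not stated | yes | yes (monthly record) |
| Side effects, tolerance, decrease in symptoms | not listed | yes | yes (monthly record) |

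Side effects and symptom change are outcomes with follow-up readings and no listed starting value.

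**Size of the overlap with pre-existing complaints**

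Inputs: n = 40 (Protocol, Methods); prevalence b of at least one complaint before cannabis, assumed to be 10% to 50% because the documents give none.

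- Expected number with a prior complaint = n × b: 40 × 0.10 = 4; 40 × 0.50 = 20.
- Chance that at least one patient has one, at b = 10%: 1 − 0.90^40 = 98.5%.

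These patients could be recorded with a side effect even if neither cannabis nor the wean caused any. The figures assume that long-standing complaints are written down when they are mentioned.

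**What a baseline would and would not repair**

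Assume independent sources with rates b (pre-existing), w (wean) and c (cannabis), with c = 10% for illustration.

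Without a baseline, the expected number recorded with any side effect is 40 × [1 − (1−b)(1−w)(1−c)]:

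- w = 0: 40 × (1 − 0.9 × 0.9) = 7.6 at b = 10%; 40 × (1 − 0.5 × 0.9) = 22.0 at b = 50%.
- w = 30%: 40 × (1 − 0.9 × 0.7 × 0.9) = 17.3 at b = 10%; 40 × (1 − 0.5 × 0.7 × 0.9) = 27.4 at b = 50%.

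With a baseline, the new-onset rate among patients free of complaints at the start is 1 − (1−w)(1−c), which no longer depends on b:

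- w = 0: 10%.
- w = 10%: 1 − 0.9 × 0.9 = 19%.
- w = 30%: 1 − 0.7 × 0.9 = 37%.

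A baseline reading therefore removes the pre-existing part. It leaves wean and cannabis effects mixed, because wean effects arise after any baseline.

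**The case against.** The strongest reply is that this is a descriptive item with no stated endpoint, and that the protocol already does part of the work. Opioid and cannabis doses are recorded monthly, so a complaint can be set against dose changes. Pain and quality of life do have baselines. The assessment list is not declared exhaustive, and the certifying physician's evaluation, whose content is not described, might pick up existing complaints. All of this is fair and keeps the point small. It does not supply the missing reading: dose records cannot show whether a complaint was already there, and an unspecified evaluation is not a planned measurement that can be compared with later visits.

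A reader might also infer more than the text supports:

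- **That prior and wean effects will be counted as cannabis effects.** The protocol says only that side effects are noted, and it states no attribution. What follows is that the sources cannot be told apart.
- **That the study fails to test its safety claim.** "Medical Cannabis is very safe and a viable option for pain relief" is a background premise under Purpose. No safety hypothesis or endpoint is stated, so no stated aim is missed.
- **That the missing baseline causes the confusion with wean effects.** It does not, as the 19% and 37% figures show.
- **That side effects are recorded only once both wean and cannabis are under way.** This rests on the order of sentences. No start dates or intervals are given.
- **That the small sample measures this problem.** With no events in 40, the exact upper limit is 8.8% (two-sided 95%: 1 − 0.025^(1/40)). That follows from n alone and would be the same with a perfect baseline.

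The rule for tabulating emergent effects, and the choice of intervals, may sit in an analysis plan that is not shown. Their absence is not criticised here.

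**Conclusion.** The point holds in a limited form. Followed as written, the protocol records side effects during follow-up with no listed reading before cannabis, in a single group of patients weaning from opioids. Complaints present at the start cannot be distinguished from new ones. Resolution of opioid side effects cannot be shown beyond what the pain and SF-36 measures reflect.

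The size rests wholly on the assumed 10% to 50% prevalence and on prior complaints being recorded when mentioned; on that basis 4 to 20 of 40 patients are affected. The pain and quality-of-life comparisons have their own baselines and are untouched. This is a cheap improvement to data collection, not a flaw that undermines the study.

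**What to change.** - Add one short side-effect checklist to the existing pre-cannabis assessment, completed before the wean starts.
- Use the same checklist at each monthly visit. A checklist at one time and free notes at another would not be comparable.
- Report effects as new, worse or resolved relative to each patient's first reading.
- Record onset dates alongside the date of first cannabis use and the dates of opioid dose changes.
- State in the protocol that wean and cannabis effects cannot be fully separated without a comparator, and describe new effects as occurring during combined wean and cannabis use.

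The cost is a few minutes per patient: 40 additional baseline checklists at an assessment that already takes place, and a structured form in place of notes at visits that already take place. No treatment, dose or visit changes.

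### The SF-36 and McGill are given only before cannabis and at month 6, so a patient lost in between has no post-baseline value on either

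*Protocol*

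**What the plan says.** The protocol's Methods section gives the assessment schedule twice. The paragraph on recruitment and inclusion/exclusion criteria lists the baseline battery ("Each participant will undergo a urine drug screen, a pain assessment using the visual analog scale and pain quality will be assessed using the SF-36", together with the McGill) and sets its timing: "prior to receiving medical marijuana and then at 6 months". The next paragraph, on certification, weaning and follow-up, repeats the final assessment: "At six months the physician will recheck a urine drug screen, current pain level and readminister the McGill Pain Questionnaire and SF-36".

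That paragraph also sets up regular contact in between: "The patient will be followed up monthly for six months by physician". The content of those visits is narrower: "he will assess the patient's pain levels and Medical Cannabis doses and opioid doses monthly". Side effects, tolerance and symptom relief are noted as well. Neither questionnaire is listed for a visit between baseline and month 6, and no assessment at early exit is described.

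The study has one group: "40 patients who have agreed to attempt wean down on opioid medication".

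**The concern.** The SF-36 and the McGill each have exactly one post-baseline time point. Whoever is lost before it drops out of the before-after comparison on that questionnaire, however many monthly visits they attended. The SF-36 is the only quality-of-life questionnaire named, and the McGill the only multidimensional pain measure. Improved quality of life is among the benefits that the Purpose section hopes for.

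With no comparison group, selective loss passes straight into the estimated change. Patients are weaning from opioids during follow-up, so loss related to poor response is plausible, though nothing in the protocol shows it. A statistical analysis plan may choose how to handle missing values. It cannot supply SF-36 or McGill scores that nobody collected, so the remedy belongs in the visit schedule.

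**Working it through.** **Schedule, side by side (protocol, Methods)**

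| Measure | Before cannabis | Months 1-5 | Month 6 |
|---|---|---|---|
| SF-36 | yes | not scheduled | yes |
| McGill | yes | not scheduled | yes |
| Urine drug screen | yes | not scheduled | yes |
| Pain level | yes | monthly | yes |
| Opioid and cannabis doses | – | monthly | monthly |

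The two paragraphs agree with each other. The gap follows from the schedule alone. The arithmetic below only sizes it.

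**Inputs.** N = 40 is from the protocol. The loss before month 6 is not stated, so d = 10%, 20%, 30% and 40% are assumed.

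**Patients affected.** With month-6 values: n = 40 × (1 − d). Leavers: L = 40 − n. Half-width of the 95% confidence interval for a mean change, in SDs of change: t(0.975, n − 1)/√n.

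| d | n | L | Half-width (SD) | Ratio to n = 40 |
|---|---|---|---|---|
| 0 | 40 | 0 | 0.320 | 1.00 |
| 10% | 36 | 4 | 0.338 | 1.06 |
| 20% | 32 | 8 | 0.361 | 1.13 |
| 30% | 28 | 12 | 0.388 | 1.21 |
| 40% | 24 | 16 | 0.422 | 1.32 |

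Today all L leavers lack a post-baseline SF-36 or McGill value: 4 to 16 patients.

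**Effect of a month-3 assessment.** If the first missed visit is equally likely to be any of months 1 to 6, the share of leavers who attend month 3 is 3/6. Those still without a value number L/2 = 2, 4, 6, 8. If two thirds of leavers reach month 3, the number is L/3 = 1.3, 2.7, 4.0, 5.3. If only one third do, it is 2L/3 = 2.7, 5.3, 8.0, 10.7.

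**Effect of an assessment at announced withdrawal.** If half of the L/2 leavers not seen at month 3 announce their withdrawal and are willing to be assessed, 1, 2, 3, 4 more are reached.

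**Possible bias (simulation on assumptions only).** Changes at months 3 and 6 are bivariate normal with SD 1 and correlation 0.5 to 0.7. The odds of leaving double per SD of worse month-3 change. Half of the loss falls before month 3 and half after it. The month-6-attender mean is compared with a regression of month 6 on month 3, applied to everyone with a month-3 value. The ranges run from d = 10%, correlation 0.5, to d = 40%, correlation 0.7.

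| How loss is modelled | Attender mean too favourable by | Using month-3 values |
|---|---|---|
| One draw of leaving over the whole follow-up | 0.035-0.176 SD | 0.017-0.067 SD |
| Doubling applied separately before and after month 3 | 0.036-0.196 SD | 0.018-0.091 SD |

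With one draw the improvement runs from 0.035 − 0.017 = 0.018 SD to 0.176 − 0.067 = 0.109 SD.

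**What the planned monthly data could already do.** If a monthly pain score correlates 0.4 to 0.6 with the month-3 questionnaire change (assumed), adjusting for it removed only about 6-19% of the bias.

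**The case against.** The strongest reply is that nothing here is in error. A before-and-after questionnaire is a coherent choice for 40 patients in one group, and the protocol states it plainly and consistently. No dropout rate is given, and nothing shows that patients doing badly would leave. They come from a pain clinic where weaning is standard care, and the protocol does not say that stopping cannabis ends follow-up. The measures closest to the study's title, opioid dose and pain, are taken monthly. No instrument is labelled primary. All of this stands, and it makes the point a suggested improvement with no contradiction behind it.

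The bias illustration is also open to challenge. It lets leaving depend on exactly the variable that the fix would collect, and its main comparison gives no credit to the monthly pain and dose data. Both criticisms are fair. The gain is smaller if later losses reflect worsening not yet visible at month 3, and part of it may already be available from the monthly data. Under the correlations assumed above, that part is modest. Even at its largest, the improvement of about 0.11 SD is well below the interval half-width of 0.34-0.42 SD.

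A reader might infer more than the protocol supports:

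- That all outcomes are lost for leavers. They are not: pain level and doses run up to the last visit attended.
- That the urine drug screen belongs in the remedy because it shares the two-point schedule ("Each participant will undergo a urine drug screen" at baseline, then a recheck). Its gap is real, but the fix does not address it.
- That the study's main result is biased. No main outcome is named, and the rate and direction of loss are unknown.
- That a missing-data method has been omitted. That may stand in an analysis plan not seen here.

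**Conclusion.** The point holds as a cheap improvement limited to the SF-36 and the McGill. That leavers have no post-baseline value on either follows directly from the Methods section and needs no assumption.

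Its size does rest on assumptions. At 10-40% loss, 4 to 16 of 40 patients are affected, falling to 2 to 8 with a month-3 assessment if losses are evenly spread. If leaving is tied to worse early change as assumed, the month-6-attender mean would be about 0.04-0.18 SD too favourable to cannabis. With month-3 values this falls to about 0.02-0.07 SD (0.04-0.20 to 0.02-0.09 SD if the link acts separately before and after month 3). These bias figures illustrate a mechanism and do not predict this study's result. Confidence is medium, because neither the rate nor the direction of loss can be read from the protocol.

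**What to change.** In the follow-up paragraph of Methods, add the SF-36 and McGill at the existing month-3 visit and, where the patient is willing, when a patient announces withdrawal from the study. The month-3 value does not replace the month-6 value. It lets the analysis use leavers' early course and compare it with that of patients who stay.

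The cost is questionnaire time (a few minutes per patient is assumed) for at most 40 extra sets at a visit already planned, plus one set per announced withdrawal. The result may come out less favourable.

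The limits should be accepted openly. The number with month-6 values stays at 36 to 24 over the assumed range, so the interval of a month-6-attender analysis is no narrower. Unannounced losses before month 3 remain unreached. The urine screen keeps its two time points. The change helps only patients who have not yet passed month 3, so it is best made before enrolment starts.
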